Participants (N = 200) who complete the HIV Medical Care Education program will be randomly assigned to a Usual Care Control group or the Incentive group. A computerized urn randomization procedure (Wei & Lachin, 1988) will be used to balance groups on five baseline characteristics that may influence outcome: (1) opiate or cocaine positive urine sample at intake to the study (Y/N); (2) Self-reported use alcohol to intoxication on 20 or more days in the past 30 on the ASI (Y/N); (3) health literacy as assessed on the TOFHLA (score \leq the rolling median, Y/N); (4) impulsivity as assessed by delay discounting (k value from the raw discounting data for each participant, which is an index of impulsivity (\leq the rolling median of k, Y/N); and (5) depression as assessed by the Beck Depression Inventory (score \leq the rolling median, Y/N). Participants will be stratified by DSM V cocaine, opiate and alcohol dependence, health literacy, and depression at intake because drug use (Mimiaga et al., 2013), health literacy (Kalichman et al., 2008), and depression (Murphy et al. 2013) has each been associated with poor ART adherence. Participants will be stratified based on measures of impulsivity because high levels of impulsivity have been associated with poor health decision making and adverse health behaviors (Axon et al. 2009; Bickel et al. 2014; Bradford et al., 2010). Participants will be taught the details of their group with written instructions and quizzes. Participants will earn up to about \$15 for answering questions on the quiz.

Incentive Group

The Incentive group will receive the novel empirically-based incentive intervention to promote long term suppression of HIV-1 RNA (viral load) being evaluated in this study. The incentive intervention will employ features and parameters that have been shown critically important to promote therapeutic behavior change in drug users and other populations (Higgins et al., 2008; Lussier et al., 2006; [name] et al., 2011). Participants will be taught the details of the incentive program with written instructions and quizzes.

A Prescription for ART. When a participant gets assigned to the Incentive group, he/she will be asked if he/she has a current prescription for ART and if he/she has at least a 2-day supply of medication. As described below, blood draws and the incentive program described below will not begin until the participant has an active ART prescription and has at least a 2-day supply of medication.

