Reloadable credit card. At the start of each participant's enrollment, each participant will be given a reloadable credit card. When the participant calls to get the results of a given viral load test, the Incentive staff will tell the participant the results. If the participant met the criterion for the incentive, the Incentive staff will tell the participant the amount of the incentive earned and add the incentive amount to the participant's reloadable credit card. This procedure will ensure that participants monitor the results of their viral load testing and know when, why and how much is added to their credit card. That card can then be used as a regular credit card to make purchases at most businesses. We currently use this reloadable credit card system in our Therapeutic Workplace incentive program, and it has proved very efficient and highly acceptable to participants.

Usual Care Control Group

Usual Care Control Only participants will receive the standard HIV medical care described above offered in their medical clinic. Participants in this group will not receive added viral load testing, feedback or incentives, beyond the viral load testing conducted as a routine part of their medical care.

Assessments

For all participants, assessments will be conducted at intake to determine eligibility and characterize participants. Outcome assessments will be conducted at intake, every 3 months throughout the 2-year intervention evaluation and every 6 months of the 1-year follow-up period. Except for the computerized delay discounting task, the assessments will be administered using the Qualtrics web-based software (<http://qualtrics.com/>) to administer and record responses for the questionnaires administered under this protocol. When necessary (e.g., if the web server is not operational), a printed version of the questions will be used.

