Intake Only Assessment Instruments. At intake we will administer: 1) BDI to screen for depression (Beck et al. 1993). 2) Test of Functional Health Literacy in Adults (TOFHLA) to measure health literacy (Parker et al., 1995). 3) A computer delay discounting task to assess impulsivity (Johnson and Bickel, 2002). In this task, on each trial the participant makes a choice between a smaller immediate reward option (e.g., \$5 now) and a larger \$10 reward delivered after a given delay (e.g., 1 week). The magnitude of the smaller immediate reward is adjusted across trials to determine an indifference point, or the amount of immediate money equal to the delayed \$10. Once an indifference point is detected, the task moves to the next of four delays (1 day, 1 week, 1 month, 6 months); 4) The Addiction Severity Index; 5) The Wide Range Achievement Test.

Intake, 3-Month and 6-month Follow-up Assessments. We may conduct these assessments at all time points: 1) HIV-1 RNA (viral load) in blood by Maryland DHMH Laboratories. 2) The presence or absence of 15 ART medications in blood (Marzinke et al., 2014). 3) We may assess blood samples that we collect for the quantitative levels of antiretroviral medications or their metabolites to determine if participants are maintaining the presumed therapeutic blood levels of the antiretroviral medications. The assessments of quantitative blood levels of antiretroviral medications could provide more information than the qualitative tests. For example, a participant could test positive for an antiretroviral medication on the qualitative test by taking the medication occasionally, but not take the antiretroviral medication often enough to maintain therapeutic blood levels of the medications. 4) blood tests of CD4 counts; 5) urine tests of drugs of abuse. 6) A

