Specific Aim. Assess the cost-effectiveness of the empirically-based incentive intervention for undetectable viral loads. We will assess incremental cost-effectiveness ratio (ICER) by dividing the difference in costs of two interventions by the difference in effects of the two interventions during the 2-year intervention evaluation period on viral load suppression (see below). The ICER can be interpreted as dollars spent per unit of desired outcomes gained. The Incentive Intervention should yield a better ICER.

Specific Aim. Assess the cost-benefit of empirically-based incentive intervention for undetectable viral loads. We will perform a Cost-Benefit Analysis (CBA) to examine the monetized benefits relative to costs for the Usual Care Control and Incentive intervention conditions. The economic outcomes are health care utilization during the 2-year intervention evaluation period (see below). We expect that the Incentive Intervention will yield greater economic benefits relative to its costs than the Usual Care Control.

Measures assessed repeatedly over time will be analyzed with a longitudinal logistic regression model. Within-person correlated outcomes will be handled using generalized estimating equations (GEE; Zeger, Liang, & Albert, 1988). Measures assessed once will be analyzed using logistic regression. The magnitude of effects will be expressed using odds ratios with 95% CI. Intent-to-treat analyses will be adjusted for covariates used for stratification (Pocock et al., 2002). Two-sided tests with p-values <.05 will be considered significant.

- b. Statistical plan including sample size justification and interim data analysis.

STATISTICAL ANALYSES

Measures assessed repeatedly over time will be analyzed with a longitudinal logistic regression model. Within-person correlated outcomes will be handled using generalized estimating equations (GEE; Zeger, Liang, & Albert, 1988). Measures assessed once will be analyzed using logistic regression. The magnitude of effects will be expressed using odds ratios with 95% CI. Intent-to-treat analyses will be adjusted for covariates used for stratification (Pocock et al., 2002). Two-sided tests with p-values <.05 will be considered significant.

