Primary outcome analyses. We will fit a longitudinal logistic regression model $\text{logit}(Y_{ij}) = \beta_0 + \beta_1 tx + \beta_{2-6}x_{2-6} + \epsilon_{ij}$, where Y_{ij} is the presence of a detectable viral load for the i th person at the j th timepoint (8 visits over two years of treatment), β_1 is the covariate of interest representing the expected decrease in log odds of a detectable viral load as a function of assignment to the treatment group, and β_{2-6} are the coefficients for the 5 randomization covariates. Additional models with time and time by treatment interactions will be fit secondarily to assess time trends in treatment effect.

Secondary outcome analyses. We will fit analogous longitudinal logistic regression models for HRMS-verified ART adherence, self-reported adherence, prescription maintenance, and attendance at HIV medical care visits. We will assess post-treatment effects by fitting analogous models for each outcome, but using only data from the two post-treatment visits.

Moderator analyses. For the primary outcome, we will fit models with interactions between treatment and each of the 5 randomization covariates (drug dependence, alcohol dependence, TOFHLA total score, delay discounting, and Beck Depression score) to assess whether treatment effect varies as a function of the putative moderator. For example, for CIDI drug dependence, we would fit the model $\text{logit}(Y_{ij}) = \beta_0 + \beta_1 tx + \beta_{2-6}x_{2-6} + \beta_7 tx * \text{drug dependence} + \epsilon_{ij}$, where β_1 would represent the treatment effect (expressed as a difference in log odds of a detectable viral load between treatment and control groups) among individuals without drug dependence, and β_7 would represent the difference in treatment effect between individuals with and without drug dependence. All moderator analyses will be considered exploratory and will not be corrected for multiple comparisons. These variables will be examined as potential moderators because drug use (Mimiaga et al., 2013), health literacy (Kalichman et al., 2008),

and depression (Murphy et al. 2013) has each been associated with poor adherence to antiretroviral medications. Impulsivity will be assessed as a potential moderator because high levels of impulsivity have been associated with poor health decision making and adverse health behaviors (Axon et al., 2009; Bickel et al. 2014; Bradford et al., 2010).

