Mediation analysis. We will assess potential mediating effects of medication adherence as assessed by qualitative blood testing on viral load using the method of Baron and Kenny (1986). Specifically, this involves estimation of (1) the effect of treatment assignment (incentives) on undetectable viral load without controlling for medication adherence, (2) the direct effect of incentives on medication adherence, and if these two steps yield clinically and statistically significant effects, 3) the effect of incentives on viral load after controlling for medication adherence ($\text{logit } (Y_{ij}) = \beta_0 + \beta_1 x_i + \beta_{2-6} x_{2-6} + \beta_7 \text{adherence} + \epsilon_{ij}$). If medication adherence does mediate the effect of the incentives on presence of a detectable viral load, in this final model we would expect the effect of treatment (β_1) to be attenuated relative to the step 1 model, and for adherence (β_7) to be a clinically and statistically significant predictor of presence of a detectable viral load.

Missing data. We expect to collect $\geq 80\%$ of 3-month assessments (see below). Our primary approach will be to impute all missing values as the adverse outcome (e.g., detectable viral load). Model parameter estimates from this approach will be compared to a method without imputation. If these methods yield differing results, conclusions will need to be tentative. To investigate sensitivity to missing values, participants with and without missing values will be compared by covariates and treatment assignment.

ECONOMIC ANALYSES

We will use the provider perspective using a modified SASCAP and the research team's financial records. Intervention activities will be captured with the modified Economic Form 90 AIR/ED.

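### Mediation step 3 adjusts non-randomised adherence only for the five randomisation covariates, so intake common causes of adherence and viremia can bias the mediation reading, in either direction

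*Combined protocol and SAP*

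**What the plan says.** Section 7b, Mediation analysis, follows the three Baron and Kenny steps: treatment on viral load, treatment on adherence and, if both effects are clinically and statistically significant, "the effect of incentives on viral load after controlling for medication adherence". The step 3 equation contains treatment, terms 2 to 6, and adherence with coefficient beta_7. Mediation is read from two signs together: the treatment coefficient is expected "to be attenuated relative to the step 1 model", and beta_7 should be a significant predictor. No proportion mediated, indirect effect or confidence interval for one is defined.

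Terms 2 to 6 are fixed under Primary outcome analyses, where beta_2-6 "are the coefficients for the 5 randomization covariates". The general rule is the same: "Intent-to-treat analyses will be adjusted for covariates used for stratification". Section 4a, Experimental Design, says the urn procedure is used to "balance groups on five baseline characteristics that may influence outcome": opiate or cocaine urine result, alcohol use to intoxication, health literacy, delay discounting and depression score.

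Other intake measures exist. Section 4a, Assessments, states "Outcome assessments will be conducted at intake, every 3 months throughout the 2-year intervention evaluation". The list for intake and follow-up names viral load, "The presence or absence of 15 ART medications in blood", CD4 count, ART refills and HIV care visits, although it is introduced with the word *may*. None of these enters step 3. The mediation text states no assumption about unmeasured confounding and plans no sensitivity analysis for it.

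**The concern.** Random assignment protects the treatment effect in steps 1 and 2. It does not protect beta_7, because participants are not randomised to adhere. Once a post-randomisation variable is conditioned on, it no longer protects the treatment coefficient either. The five covariates were chosen to balance the groups. None describes HIV disease state, prior ART exposure or engagement in care.

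Variation in these is built into the entry criteria: section 5 admits people not receiving HIV care alongside people in care for at least 12 weeks, and the Incentive Group section checks whether a participant has a current ART prescription. Being out of care or without a prescription at entry plausibly predicts both later non-adherence and later viremia. Such a factor would strengthen beta_7 and shrink beta_1, which are the two signs the plan takes as evidence of mediation.

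Mediation through adherence is a listed secondary objective. Unlike the moderator analyses, it is not labelled exploratory. At stake is how much of any incentive effect is credited to adherence.

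**Working it through.** The plan gives no number for mediation, so there is no figure to reproduce. The calculation below only illustrates direction and possible size; **every input is an assumption**.

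**Model.** One visit, 1:1 allocation, one standardised intake factor L ~ N(0,1) left out of the plan's model:

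- logit P(adherent) = -0.2 + 1.0·tx - a·L
- logit P(detectable) = 1.0 - 0.3·tx - 1.8·adherent + b·L

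The true direct effect is -0.30 and the true adherence coefficient is -1.80. Adherence is measured without error. The coefficients are large-sample values obtained by numerical integration over L, so they carry no simulation noise.

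**Quantity.** The plan's own reading, expressed as a percentage: attenuation = 1 - beta_1(step 3) / beta_1(step 1). It is computed without L, as planned, and with L in both steps.

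| a, b | Step 1, no L | Step 3, no L | beta_7, no L | Attenuation, no L | Step 1, with L | Step 3, with L | Attenuation, with L |
|---|---|---|---|---|---|---|---|
| 0, 0 | -0.658 | -0.300 | -1.80 | 54% | -0.658 | -0.300 | 54% |
| 0.5, 0.5 | -0.603 | -0.235 | -1.94 | 61% | -0.656 | -0.300 | 54% |
| 0.8, 0.8 | -0.541 | -0.162 | -2.11 | 70% | -0.652 | -0.300 | 54% |
| 1.2, 1.2 | -0.459 | -0.066 | -2.40 | 86% | -0.646 | -0.300 | 54% |
| 0.5, -0.5 | -0.623 | -0.337 | -1.48 | 46% | -0.631 | -0.300 | 52% |
| 0.8, -0.8 | -0.579 | -0.375 | -1.10 | 35% | -0.604 | -0.300 | 50% |

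Example, second row: 1 - 0.235/0.603 = 0.61 without L; 1 - 0.300/0.656 = 0.54 with L.

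**Direction.** Rows 2 to 4 are causes that lower adherence and raise viremia: beta_7 is overstated and beta_1 shrinks too far. Rows 5 and 6 are causes that lower adherence and lower viremia: both errors reverse. The opposite-sign case is not far-fetched here. Section 5 requires a detectable viral load at entry, so a participant with ART in the blood at intake is viremic despite drug, which may predict both more pill-taking and more viremia later.

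**Second set of assumptions.** Control adherence 50%, control detectability 60%, incentive effect on adherence 0.9 log odds, direct effect -0.3, equal strengths of 0.5 and 1.0 log odds per SD on both paths.

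- Adverse on both paths: 46-66% without the factor against 37-38% with it (adherence coefficient -1); 58-72% against 51-52% (adherence coefficient -2).
- Opposite signs: 6-29% against 35-37%; 28-45% against 47-50%.
- A factor acting on only one path moves the result by at most about 2 points.

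The bias therefore needs a cause of both adherence and viremia, and its sign follows the signs of the two paths.

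**The case against.** Five points can be made for the plan.

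1. *The five covariates already cover some common causes.* Drug use, literacy and depression were chosen for their association with poor ART adherence. This stands in part: what remains after them may be weaker than assumed. At 0.3 log odds on both paths the reading moves only from 54% to 57%. But none of the five measures prior ART use, care status or viral load.

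2. *The direction is not known.* This stands. A reader might infer that the omitted factors must inflate the apparent role of adherence. The documents do not support that, for the reason given about entry viremia.

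3. *The alarming case needs strong confounding.* This also stands. A reader might infer that the trial would credit adherence with nearly all of the effect. The 86% figure needs 1.2 log odds per SD on both paths, an odds ratio of exp(1.2) = 3.3 each, and nothing in the documents points to that strength.

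4. *Another bias works the other way.* Section 4a concedes that occasional pill-taking can give a positive qualitative test. With an assumed 20% false-positive rate among non-adherent participants, the plan's model gives 39%, 44% and 52% at strengths 0.5, 0.8 and 1.2, all below 54%. Adding L then moves the direct effect away from the true -0.30: from -0.37 to -0.43 at 0.5, and from -0.30 to -0.43 at 0.8. So adjustment cannot be promised to recover the true direct effect. This is a separate error, however, and the chance that two errors partly cancel is no reason to leave one in place.

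5. *The analysis is secondary and conditional on steps 1 and 2.* True, and it limits the consequence. It does not make step 3 interpretable.

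**Conclusion.** The point holds as a risk of bias without a certain sign. Step 3 conditions on a non-randomised mediator, adjusts only for covariates chosen for randomisation balance, and leaves out intake measures that the protocol lists and that plausibly affect both adherence and viremia. Nothing else in the plan addresses this.

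Under the first set of assumptions the plan's reading is too high by about 7 to 32 points (61 - 54 and 86 - 54) when the cause is adverse on both paths, and too low by about 6 to 15 points (52 - 46 and 50 - 35) when the signs are opposite. These sizes rest on assumed strengths, a single omitted factor, one visit and an error-free mediator. The plan's attenuation is also a ratio of logistic coefficients from different models and should not be taken as a proportion mediated. The randomised comparisons in the primary analysis and in mediation steps 1 and 2 are not compromised. The change is worth making before analysis because the aim is a stated objective and the remedy is cheap.

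**What to change.** In section 7b, Mediation analysis:

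- Use one covariate set in all three steps: the five randomisation covariates plus intake log10 viral load, intake drug-in-blood (HRMS) result, and intake ART prescription and care status. Confirm which were in fact collected at intake; a detectable viral load is an entry criterion, but the assessment list is worded as optional.
- Leave the primary model unchanged.
- Do not add post-randomisation viral loads as ordinary covariates, since treatment affects them.
- State the assumption of no unmeasured confounding between adherence and viral load, and report how strong an unmeasured common cause would have to be to explain away beta_7.
- When interpreting the result, state that false-positive adherence tests and post-randomisation confounders remain as sources of bias.

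The cost is plan wording and a few model terms. The mediation step 1 odds ratio will differ slightly from the primary one, which needs a sentence of explanation. Any participant without an intake value will need a stated handling rule.

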a. Medical risks, listing all procedures, their major and minor risks and expected frequency.

There is essentially no risk above those of normal daily living associated with the incentives, or with the data collection procedures used in these studies.

Blood samples will be collected from participants in the Incentive group. Those participants will provide a maximum of 1 blood sample per week. The samples will be tested for viral load and will involve collecting up to 10 cc of blood per sample. Participants in both groups will provide blood samples every 3 months for the primary and secondary outcome measures. Each of those samples (25 cc in total) will be tested for viral load (10 cc), for the presence of antiretroviral medications (5 cc), and for CD4 Counts (10 cc). Taking blood may cause some discomfort, bleeding or bruising where the needle enters the body, and in rare cases, it may result in fainting. There is a small risk of infection. When possible, we will use data available in each participant's medical records to get recent viral load and CD4 counts measures instead of collecting blood samples at each assessment time point.

b. Steps taken to minimize the risks.

To protect confidentiality, all research participants are identified by participant identification codes (Participant IDs) consisting of their initials and sequentially-assigned participant numbers on most forms and data files, and not by their names. Picture ID cards are maintained by staff in a locked container, and kept in a locked, secured area when not in use. All research data are stored in locked areas accessible only to research staff and are not left unattended. Documents with confidential information are shredded before being discarded. Confidential information is never given to anyone outside of the research program without the explicit written permission of the research participant. Only selected designated staff members are approved to give confidential information out after obtaining explicit written permission from the

participant. All research staff are trained in these procedures. We collect only general information about participant activities, legal and illegal. We do not collect information about specific illegal acts. To further protect confidentiality, we will obtain a confidentiality certificate from NIH to protect data collected in this study.

c. Plan for reporting unanticipated problems or study deviations.

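### Read literally, the adverse-outcome imputation rule scores a missing HRMS test as non-adherent when HRMS is the mediator, which can bias the adherence coefficient (β₇) in either direction

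*Combined protocol and SAP*

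**What the plan says.** All references are to the combined protocol and SAP.

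- **Section 7b, Missing data.** The rule is "Our primary approach will be to impute all missing values as the adverse outcome (e.g., detectable viral load"; viral load is given only as an example. Two checks follow: "Model parameter estimates from this approach will be compared to a method without imputation", and "participants with and without missing values will be compared by covariates and treatment assignment". If the methods disagree, conclusions are to be tentative.
- **Section 7b, Mediation analysis.** Step 1 estimates the effect of incentives on viral load, and step 2 their effect on adherence. Then, "if these two steps yield clinically and statistically significant effects", step 3 estimates "the effect of incentives on viral load after controlling for medication adherence". Mediation is read from attenuation of β₁ between steps 1 and 3, together with a clinically and statistically significant β₇.
- **Section 7a, Secondary outcome variables.** HRMS adherence is a Y/N outcome at each 3-month assessment, positive only if every prescribed drug is found.
- **Risks, a. Medical risks.** One 3-monthly sample "will be tested for viral load (10 cc), for the presence of antiretroviral medications (5 cc), and for CD4 Counts (10 cc". Where possible, medical records are used "to get recent viral load and CD4 counts measures instead of collecting blood samples at each assessment time point". HRMS is not among the measures taken from records.
- **Section 4a, Assessments.** The wording is permissive: "We may conduct these assessments at all time points".
- **Section 4a, COVID-19 Procedures.** Remaining assessments have no in-person contact, and clinic results are obtained where possible. No other source for HRMS is named.

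**The concern.** Scoring a missing result as failure is a familiar convention for an outcome. For a covariate it is misclassification: a test not run because staff used a clinic record says nothing about adherence.

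Two patterns of loss are foreseeable, and they push β₇ in opposite directions.

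- **Both tests lost.** A missed draw is scored non-adherent and detectable at once. This adds visits on which the two agree by construction and moves β₇ away from zero.
- **HRMS only lost.** Viral load comes from records and no antiretroviral tube is drawn. Some adherent participants are moved into the non-adherent group with their true viral load, which pulls a real association toward the null. The documents do not say whether the tube is still drawn at such visits.

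At stake is how much of any incentive effect is credited to adherence, which is a stated secondary objective (section 2).

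**Working it through.** **The plan's own figure.** Power Analysis: 200 × 0.80 = 160, which reproduces. The 20% is one overall rate for uncollected assessments, not split by arm or by test. No expected β₇ is given, so the adherence and suppression rates below are assumptions.

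Odds ratios (ORs) for adherence are odds of a detectable viral load, non-adherent versus adherent, exp(−β₇). Those for treatment are control versus Incentive, exp(−β₁).

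**1. No true link.** Let a = proportion adherent, d = proportion detectable, m = proportion of visits missing HRMS, and v = share of those visits with viral load available. After the rule is applied the cells are:

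- adherent, detectable: a·d·(1−m)
- adherent, suppressed: a·(1−d)·(1−m)
- non-adherent, detectable: (1−a)·d·(1−m) + m·(1−v) + m·v·d
- non-adherent, suppressed: (1−a)·(1−d)·(1−m) + m·v·(1−d)

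With m = 0.20 and v = 0, a true OR of 1.0 becomes:

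- a = 0.5, d = 0.5: (0.40 × 0.20)/(0.20 × 0.20) = 2.0
- a = 0.6, d = 0.4: (0.328 × 0.288)/(0.192 × 0.192) = 2.6
- a = 0.7, d = 0.3: (0.272 × 0.392)/(0.168 × 0.168) = 3.8

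With v = 0.5 these are 1.4, 1.6 and 2.0. With v = 1 the OR stays 1.0.

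**2. Real link.** Assumed: adherence 40% control and 65% Incentive; suppression 20% if non-adherent and 75% if adherent; 8 points added directly by Incentive.

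- Suppression is 0.40 × 0.75 + 0.60 × 0.20 = 0.42 in control and 0.65 × 0.83 + 0.35 × 0.28 = 0.6375 in Incentive.
- Step-1 OR = (0.6375/0.3625)/(0.42/0.58) = 2.43.
- Logistic step-3 fit to the exact cell probabilities: treatment OR 1.59, adherence OR 12.3.
- Share explained = 1 − ln(1.59)/ln(2.43) = 48%. This summarises the attenuation that the plan names; the plan itself defines no such share.

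Hand check at 20% missing in each arm:

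- Both lost, control: (0.584 × 0.24)/(0.096 × 0.08) = 18.3, true value 12.0. Incentive: (0.4016 × 0.4316)/(0.0784 × 0.0884) = 25.0, true value 12.6. Step-3 fit: 21.4.
- HRMS only, control: (0.50 × 0.24)/(0.18 × 0.08) = 8.3. Incentive: (0.2741 × 0.4316)/(0.2059 × 0.0884) = 6.5. Step-3 fit: 7.3.

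Adherence OR and share explained under the rule (truth 12.3 and 48%):

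| Missing, control/Incentive | Both lost | Viral load at half | HRMS only |
|---|---|---|---|
| 20%/20% | 21.4; 55% | 11.7; 38% | 7.3; 27% |
| 25%/15% | 20.9; 51% | 11.8; 46% | 7.5; 41% |
| 30%/10% | 20.1; 48% | 11.9; 54% | 7.9; 56% |
| 15%/25% | 21.8; 63% | 11.6; 26% | 7.3; 13% |

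Visits with both tests observed return about 12.3 and 48% at every split. With HRMS-only loss of 5% or 10% in each arm, the OR is 10.4 or 9.1 and the share 41% or 35%.

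**3. Other assumed inputs.** Adherence 50% control and 65–75% Incentive; undetectable 40% and 54–55%; partial mediation; 20% missing per arm. Joint loss moves the OR from 17 to 29 with attenuation 47% to 48%. HRMS-only loss moves it from 17 to 7.4 with attenuation 47% to 25%.

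**4. Verdicts.** Simulated trials used N = 200, 8 visits, independence GEE with robust errors, an assumed within-person correlation of about 0.39 and 600 runs per scenario. With the real link of item 2, mediation is found in 98–100% both under the rule and on observed pairs, and verdicts differ in 0–2%. The interquartile range of the share on observed pairs is about 36–62%. These simulated figures have not been independently repeated.

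**5. Outcome-dependent loss.** Assume that control loses both tests at 15% of suppressed and 35% of detectable visits, and Incentive at 15% throughout. The step-1 OR of 2.43 becomes 2.13 imputed and 1.86 unimputed. The share is about 68% in both, against a true 48%.

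**The case against.** **The rule may mean outcomes only.** Its wording speaks of an adverse outcome, and in step 3 adherence is a covariate. This reading is possible. But HRMS is the step-2 outcome, so an imputed value carries naturally into step 3. If it does not, the plan has no stated primary rule for a missing mediator. Clarifying text is needed either way.

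**The plan already guards against this.** It compares parameter estimates, not only verdicts, with an unimputed analysis and checks missingness by arm. That stands as real protection when missingness is unrelated to outcome. It is partial: the adverse-imputed version remains primary, the only consequence is a tentative reading, and under item 5 the two analyses agree on a wrong share. Observed pairs share that last weakness.

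**The HRMS-only rate is assumed.** Correct. A visit with viral load from records counts as collected for the primary outcome, so the plan's 20% is not a rate for this pattern.

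**Stronger readings that the documents do not support.** A reader might infer that the reported size of mediation must be wrong. It need not be: the share is 48% with joint loss at 30%/10% and 47% at 20%/20% if viral load is available at one fifth of the missed visits, and the OR is 11.7 when it is available at half. A reader might also infer that the rule will manufacture mediation. In simulation that was frequent (62–73% with joint loss, against 1–3% on observed pairs) only when incentives moved adherence and viral load by 15 points each with no link between them. That contradicts the premise in section 7a that suppression requires adherence, and the planned comparison would expose it.

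**Conclusion.** The rule is wrong as written for the mediation analysis: a minor-to-moderate point on a secondary aim. Applied literally, it can materially bias β₇, away from zero when both tests are lost and toward zero when only HRMS is lost and a real link exists. In the worked example at 20% missing per arm, that is a factor of 21.4/12.3 = 1.7 or 7.3/12.3 = 0.6.

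The error in β₁ attenuation has no fixed direction and may be negligible. At 20%/20% the joint-loss share (55% against 48%) lies inside the simulated interquartile range. The HRMS-only share (27%) lies outside it; at 10% it is near the edge (35%), and at 5% inside (41%).

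These sizes rest on assumed adherence, suppression and missingness rates and on models without baseline covariates. The documents do not give the mix of missing patterns or the number of tests affected by the COVID procedures. The primary treatment comparison does not use HRMS, so nothing here bears on it.

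**What to change.** In section 7b:

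1. State that adverse imputation applies to outcomes and not to HRMS as the mediator. It can stay for HRMS as a secondary outcome.
2. Fit steps 1 to 3 on the same visits, those with both HRMS and viral load measured. Alternatively, use joint multiple imputation of both given arm, earlier results and covariates.
3. Treat HRMS tests not taken because records or the COVID procedures replaced the draw as missing, not as non-adherent.
4. Keep the adverse-imputed mediation model as a sensitivity version. Report β₇ and the step-1 and step-3 β₁ side by side, with counts of each missing pattern by arm, and state which estimate is the main one.

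The cost is wording and some programming; the primary analysis is unchanged. Observed pairs use about 20% fewer records at the plan's missing rate, and they remain biased if missingness depends on both arm and outcome.
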